3.1.1.4. Adverse Events

AEs will be categorized according to MedDRA terms. AEs will be collected from the signing of the ICD through Visit 3 (approximately 1 month after Visit 2). The primary-endpoint AEs within 1 month after each vaccination will be summarized by system organ class and preferred term on a participant level.

This primary endpoint will be supported by summaries and listings of related AEs, severe AEs, and immediate AEs (start time is within the first 30 minutes after vaccination).

AE reporting will be based on the specific reporting period. Missing AE start dates will be imputed following the Pfizer data standard rules as described in [Section 5.3](#).

A 3-tier approach will be used to summarize AEs within 1 month after each vaccination. Under this approach, AEs are classified into 1 of 3 tiers. Different analyses will be performed for different tiers (see [Section 6.1.1.3.1](#)).

- Tier 1 events: These are prespecified events of clinical importance and are identified in a list in the product’s Safety Review Plan. No Tier 1 events have been identified to date for 20vPnC.
- Tier 2 events: These are events that are not Tier 1, but are “relatively common.” A MedDRA preferred term is defined as a Tier 2 event if there are at least 1% of participants in at least 1 vaccine group reporting the event.
- Tier 3 events: These are events that are neither Tier 1 nor Tier 2.

3.1.1.5. Serious Adverse Events and Newly Diagnosed Chronic Medical Conditions

SAEs and NDCMCs will be categorized according to MedDRA terms. NDCMCs and SAEs will be collected from the signing of the ICD through the end of the study.

3.1.2. Primary Pneumococcal Immunogenicity Endpoint

- Pneumococcal serotype-specific OPA titers 1 month after vaccination with 20vPnC.

OPA titers for the 20 pneumococcal serotypes (1, 3, 4, 5, 6A, 6B, 7F, 8, 9V, 10A, 11A, 12F, 14, 15B, 18C, 19A, 19F, 22F, 23F, and 33F) will be determined for all participants' sera collected at Visit 1 (prior to administration of SIIV and blinded vaccine), Visit 2 (1 month after administration of vaccines at Visit 1, and prior to blinded vaccine at Visit 2), and Visit 3 (1 month after vaccination at Visit 2).

OPA titers above the LLOQ are considered accurate and their quantitated values will be reported. OPA titers below the corresponding LLOQ or denoted as BLQ will be set to $0.5 \times$ LLOQ for analysis. Missing assay results will not be imputed.

3.1.3. Primary SIIV Immunogenicity Endpoint

- Strain-specific HAI titers 1 month after vaccination with SIIV

HAI titers to the influenza strains (A/H1N1, A/H3N2, B/Victoria, and B/Phuket) in the SIIV administered will be determined on sera collected at Visit 1 (prior to administration of SIIV and blinded vaccine) and Visit 2 (1 month after SIIV administration at Visit 1).

HAI titers above the LLOQ are considered accurate and their quantitated values will be reported. HAI titers below the corresponding LLOQ or denoted as BLQ will be set to $0.5 \times$ LLOQ for analysis. Missing assay results will not be imputed.

3.2. Secondary Endpoints

3.2.1. Secondary Pneumococcal Immunogenicity Endpoints

- Pneumococcal serotype-specific OPA titers and fold rises in OPA titers from before vaccination to 1 month after vaccination with 20vPnC
 - The fold rises will be the ratio of OPA titers at Visit 2 to Visit 1 for the (SIIV+20vPnC)/saline group and the ratio of OPA titers at Visit 3 to Visit 1 for the (SIIV+saline)/20vPnC group.
- Classification of fold rise in OPA titers from before vaccination to 1 month after vaccination with 20vPnC as a ≥ 4 -fold rise

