4. STUDY DESIGN

4.1. Overall Design

[figure not shown]
This Phase 3, multicenter, randomized, double-blind study, with a 2-arm parallel design, will be conducted at investigator sites in the United States. The purpose of this study is to assess the safety and immunogenicity of 20vPnC and SIIV when given together at the same visit ([SIIV+20vPnC]/saline group) compared to 20vPnC given 1 month after SIIV ([SIIV+saline]/20vPnC group). The study design and assessments are modeled from prior studies of pneumococcal conjugate vaccine coadministered with influenza vaccine.^{68,69,70}

CCI [REDACTED]

Approximately 1780 healthy adults ≥ 65 years of age will be stratified by prior pneumococcal vaccine status (no previous pneumococcal vaccine [naïve], receipt of at least 1 dose of PPSV23 only, receipt of at least 1 dose of 13vPnC only, or receipt of at least 1 dose each of PPSV23 and 13vPnC) and randomized in 1:1 ratio to 1 of 2 groups by center-based randomization. The coadministration group ([SIIV+20vPnC]/saline) will receive SIIV and 20vPnC at the same visit (Visit 1), followed 1 month later by administration of saline (Visit 2). The separate-administration group ([SIIV+saline]/20vPnC) will receive SIIV and saline at Visit 1, followed 1 month later with 20vPnC administered at Visit 2.

Refer to [Section 4.2](#) for the rationale behind this stratification.

If participants have received prior pneumococcal vaccination(s), the most recent dose must have been given ≥ 6 months prior to the first study vaccination. Information on any prior pneumococcal vaccines will be collected at enrollment. **CCI**

On Day 1 (Visit 1), participants will be assessed for eligibility (including medical history and pneumococcal vaccine history). If eligible, participants will have blood drawn for immunogenicity assessments and be randomized to receive either SIIV and 20vPnC ([SIIV+20vPnC]/saline) or SIIV and saline ([SIIV+saline]/20vPnC). The 20vPnC and saline will be prepared and administered by an unblinded investigator site staff member. Participants will be observed for 30 minutes after vaccination by blinded investigator site staff, and any reactions occurring during that time will be recorded as AEs.

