5.5.1. Temporary Delay Criteria

The following conditions are temporary or self-limiting and a participant may be vaccinated in the study once the condition(s) has/have resolved and no other exclusion criteria are met.

The Visit 1 and Visit 2 blood draws prior to vaccination should take place on the same day as the vaccination.

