8.1. Efficacy and/or Immunogenicity Assessments

8.1.1. Immunogenicity Assessments

Blood samples (approximately 30 mL) will be collected from all participants at Visit 1 (prior to administration of SIIV and blinded vaccine), Visit 2 (1 month [28 to 42 days] after administration of vaccines at Visit 1, and prior to blinded vaccine at Visit 2), and Visit 3 (1 month [28 to 42 days] after vaccination at Visit 2). Sample collection, processing, storage, and shipping information can be found in the SRM or equivalent manual.

Pneumococcal Responses

OPA Responses to the 20vPnC Serotypes

OPA titers for the 20vPnC serotypes will be measured in sera collected at Visits 1, 2, and 3.

SIIV Responses

HAI titers to the influenza strains in the SIIV administered will be determined on sera collected at Visits 1 and 2 (prior to and 1 month [28 to 42 days] after SIIV administration).

CCI [REDACTED]

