- The investigator or appropriately qualified designee reviews the e-diary data online at frequent intervals (daily is optimal) for the 10 days (Day 1 is the day of vaccination) following vaccination to evaluate participant compliance and as part of the ongoing safety review.

8.11.2. Visit 2 (Vaccination 2 – 28 to 42 Days After Visit 1 [Study Days 29 to 43])

Prior to vaccination:

- Ensure and document that the participant continues to be eligible for the study (see [Section 7](#) for participant discontinuation/withdrawal) and that none of the temporary delay criteria are met.
- Record nonstudy vaccinations as described in [Section 6.6](#).
- Perform a contraception check (see [Section 10.4](#)), if applicable.
- Review the participant's e-diary data. Collect stop dates of any e-diary events (local reactions or systemic events) ongoing on the last day that the e-diary was completed and record stop dates in the CRF.
- Determine if any AEs (includes nonserious AEs, SAEs, and NDCMCs) have occurred since the previous visit, follow up on any previously reported events to determine the outcome (ie, record stop dates or confirm if they are still continuing), record as described in [Section 8.2](#), and record concomitant medications used to treat NDCMCs and SAEs.
- Measure and record the participant's oral temperature (°F/°C).
- Collect a blood sample of approximately 30 mL for immunogenicity assessments prior to vaccination.

After vaccination (including investigational product administration):

- An unblinded site staff member will administer a single 0.5-mL injection of 20vPnC or saline into the deltoid muscle of the left arm.
- Blinded site staff will observe the participant for 30 minutes after investigational product administration for any acute (immediate) reactions. Record any acute (immediate) reactions on the AE CRF and on an SAE form, as applicable.

- Confirm that the e-diary is working and review instructions, if necessary. Ask the participant to complete the e-diary from Day 1 to Day 10, with Day 1 being the day of vaccination. Provide thermometer or measuring device, if needed.

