- Ask the participant to contact the investigator site staff or investigator as soon as possible during the 10-day postvaccination period if the participant has redness and/or swelling at the 20vPnC or saline injection site measuring >20 measuring device units (>10.0 cm), or severe 20vPnC or saline injection site pain (prevents daily activity) to determine if the event requires further assessment by the investigator (refer to [Section 10.3](#)).
- Ask the participant to contact the investigator site staff or the investigator as soon as possible if they experience any possible Grade 4 prompted local reaction in their left arm within 10 days, or systemic event within 7 days, after vaccination (refer to [Section 8.3](#)).
- Ask the participant to contact the site staff or investigator immediately if any significant illness or medical event (eg, emergency room visit or hospitalization) occurs.
- Inform the participant that they may be contacted by site staff to obtain additional information on reports of fever >102.0°F or Grade 3 events entered into the e-diary.
- Inform the participant that use of prophylactic antipyretic/pain medication, while permitted, is not recommended on the day of investigational product administration (before or after vaccination).
- Remind the participant to use appropriate contraceptives until 28 days after vaccination, if applicable.
- The investigator or an authorized designee completes the CRF and the source documents and updates the investigational product accountability records.
- The investigator or appropriately qualified designee reviews the e-diary data online at frequent intervals (daily is optimal) for the 10 days (Day 1 is the day of vaccination) following vaccination to evaluate participant compliance and as part of the ongoing safety review.

8.11.3. Visit 3 (Follow-up – 28 to 42 Days After Vaccination 2 [Study Days 57 to 85])

- Ensure and document that the participant continues to be eligible for the study (see [Section 7](#) for participant discontinuation/withdrawal).
- Record nonstudy vaccinations as described in [Section 6.6](#).
- Review the participant's e-diary data. Collect stop dates of any e-diary events (local reactions or systemic events) ongoing on the last day that the e-diary was completed and record stop dates in the CRF.

- Collect the e-diary (if applicable).

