6.2. Secondary Endpoints

6.2.1. Secondary Pneumococcal Immunogenicity Endpoints

6.2.1.1. Fold Rises in Pneumococcal Serotype-Specific OPA Titers 1 Month After Vaccination With 20vPnC

- Estimand:
 - GMFR in serotype-specific OPA titers from before to 1 month after 20vPnC.
- Analysis set: Evaluable pneumococcal immunogenicity population. CCI [redacted]
- Analysis time point: 1 Month after vaccination with 20vPnC.
- Analysis methodology: Descriptive statistics ([Section 5.2.2.3](#)).
- Reporting results: For each of the 20 vaccine serotypes, the number of participants (n), GMTs at before and 1 month after vaccination, GMFRs from before vaccination to 1 month after vaccination, and the corresponding 2-sided 95% CIs for serotype-specific OPA titers will be presented for each vaccine group.

6.2.1.2. Participants With a ≥ 4 -Fold Rise in Serotype-Specific OPA Titers From Before to 1 Month After 20vPnC

- Estimand:
 - The percentage of participants with a ≥ 4 -fold rise in serotype-specific OPA titers from before vaccination to 1 month after vaccination.
- Analysis set: Evaluable pneumococcal immunogenicity population. CCI [REDACTED]
- Analysis time point: 1 Month after vaccination with 20vPnC.
- Analysis methodology: Descriptive statistics (Section 5.2.2.3).
- Reporting results: The proportion of participants with a ≥ 4 -fold rise from before vaccination to 1 month after vaccination and associated 95% CI for the 20 matching serotypes will be summarized by vaccine group. The number of participants (n) and the denominator (N) used in the percentage calculation, the percentage (%), and the corresponding 95% Clopper-Pearson CI will be presented by vaccine group as well.

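### Should the separate group's OPA fold rise start from the Visit 2 sample drawn just before 20vPnC instead of from Visit 1?

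*SAP*

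**What the plan says.** SAP 3.2.1 gives one rule per group. For coadministration: "The fold rises will be the ratio of OPA titers at Visit 2 to Visit 1 for the (SIIV+20vPnC)/saline group". For separate administration: "the ratio of OPA titers at Visit 3 to Visit 1 for the (SIIV+saline)/20vPnC group". SAP 6.2.1.1 words the estimand as "GMFR in serotype-specific OPA titers from before to 1 month after 20vPnC".

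Under Protocol 4.1, the separate-administration group "will receive SIIV and saline at Visit 1, followed 1 month later with 20vPnC administered at Visit 2". Protocol 8.1.1 states that "OPA titers for the 20vPnC serotypes will be measured in sera collected at Visits 1, 2, and 3", and Protocol 5.5.1 adds: "The Visit 1 and Visit 2 blood draws prior to vaccination should take place on the same day as the vaccination". An OPA titer from immediately before 20vPnC is therefore planned in both groups: from Visit 1 under coadministration and from Visit 2 under separate administration.

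Two other places matter. SAP 3.4 makes the pre-vaccination Day 1 sample the baseline for the assessments. The secondary pneumococcal rows in Protocol 3 and 9.4.1 speak of the time before vaccination without naming a visit.

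**The concern.** The secondary objective is to describe the rise in response to 20vPnC. In the separate group a same-day pre-20vPnC titer exists, yet the denominator is a titer taken a visit earlier. That group's ratio then covers about two months instead of one. It also absorbs whatever happens to OPA titers between Visits 1 and 2, such as an effect of SIIV, natural exposure, waning or assay variation.

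The GMFR and the percentage with a ≥4-fold rise are the secondary OPA results listed in the visible text, and they are tabulated by vaccine group. If the extra month distorted one column, readers comparing the columns could be misled about coadministration.

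**Working it through.** **1. Interval lengths.** The inputs are the visit windows in the headings of Protocol 8.11.2 ("28 to 42 Days After Visit 1 [Study Days 29 to 43") and 8.11.3 ("28 to 42 Days After Vaccination 2 [Study Days 57 to 85").

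- Coadministration, Visit 1 to Visit 2: 28 to 42 days.
- Separate, Visit 1 to Visit 3: 28 + 28 = 56 to 42 + 42 = 84 days. With Day 1 as the first vaccination day this is Study Days 57 to 85, which reproduces the protocol's figure.

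The difference in duration is real.

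**2. Definition against estimand wording.** Visit 1 is before 20vPnC in both groups, and Visit 2 (coadministration) and Visit 3 (separate) are each 1 month after it. The ratio therefore does run from before 20vPnC to 1 month after it. The wording does not require the last sample before the injection. SAP 3.2.1, 3.4 and 6.2.1.1 agree with each other.

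**3. What the side-by-side comparison estimates.** Write C for coadministration, S for separate, and V1 to V3 for the visit GMTs, among participants with the required results.

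- Under the SAP: GMFR(C) / GMFR(S) = [C(V2)/C(V1)] / [S(V3)/S(V1)] = [C(V2)/S(V3)] × [S(V1)/C(V1)].
- The first factor is the contrast of the primary GMR (SAP 6.1.2.1). The second is 1 in expectation, because Visit 1 blood is drawn before any study vaccine in randomized groups.
- With Visit 2 as the separate group's denominator: [C(V2)/C(V1)] / [S(V3)/S(V2)] = [C(V2)/S(V3)] × [S(V2)/C(V1)]. Let d = S(V2)/S(V1). The second factor is then d in expectation.

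Switching the denominator does not remove the Visit 1 to Visit 2 change. It takes d out of one group's column and puts it into the comparison between columns, which would then differ from the primary GMR by the factor d.

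**4. Where SIIV falls.**

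| Separate group's denominator | Interval, coadministration | Interval, separate | SIIV inside interval, coadministration | SIIV inside interval, separate |
|---|---|---|---|---|
| Visit 1 (SAP) | 28–42 days | 56–84 days | yes | yes |
| Visit 2 | 28–42 days | 28–42 days | yes | no, given 28–42 days earlier |

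As planned, both ratios run from before any study vaccine to 1 month after 20vPnC. The alternative matches duration but leaves SIIV in one interval only.

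**5. Size.** The documents give no value for d, so 0.9 to 1.1 is an assumption. For participants with all three results, GMFR(V3/V1) = GMFR(V3/V2) × d, so the reported GMFR is 10% lower to 10% higher than Visit 3/Visit 2.

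For the ≥4-fold percentage, assume a normal ln fold rise with mean ln G and SD s, so that P = Φ((ln(G·d) − ln 4)/s):

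| G | s | d = 0.9 | d = 1 | d = 1.1 |
|---|---|---|---|---|
| 6 | 1.6 | 57.4% | 60.0% | 62.3% |
| 4 | 1.4 | 47.0% | 50.0% | 52.7% |

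The shift is about 2 to 3 points. At d = 0.8 or 1.25, with G from 3 to 12 and s from 1.5 to 2.0, it is about 4 to 6 points.

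For scale, with the planned 800 evaluable participants per group (Protocol 9.2), the 95% half-width of a percentage near 50% is 1.96 × √(0.25/800) = 3.5 points. For a GMFR, exp(1.96 × s/√800) with s = 1.4 to 1.6 gives 1.10 to 1.12, or 10% to 12%. A shift is systematic and does not average out, so this shows only its order of magnitude.

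**The case for a change.** The strongest case for Visit 2 is that the objective describes a response to 20vPnC, and the sample closest to the injection isolates that response best. The SIIV fold rise in SAP 3.2.2 uses the immediate pre-dose sample in both groups, so OPA in the separate group is the one exception. The titers are already planned, so a change would cost only wording. The visible text gives no reason for choosing Visit 1 and no separate-group change from Visit 1 to Visit 2, so a reader could not see whether the extra month mattered.

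Part of this stands. The intervals do differ, a Visit 3/Visit 2 ratio would be a legitimate supportive description, and no rationale is stated. But the exception follows from the design: Visit 1 is the immediate pre-dose sample for everything given at Visit 1, and only 20vPnC in the separate group comes later. Visit 3/Visit 2 has its own asymmetry, since it divides one group by a titer taken after randomization and after SIIV. Nor can it be said that the plan leaves the Visit 2 sample unused, because redacted text directly follows the secondary endpoint definitions and analyses and may use it.

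**Conclusion.** The concern does not hold. The SAP states the fold rise openly for each group, in agreement with its own baseline definition and estimand wording. A common Visit 1 denominator keeps the side-by-side GMFRs in line with the primary GMR and keeps SIIV inside both intervals. Visit 2 trades those properties for equal duration, which makes it an alternative and not a correction.

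The effect on the separate group's own figures is a 10% shift in GMFR and about 2 to 3 percentage points, if titers change by a factor of 0.9 to 1.1 before 20vPnC. If they do not change, it is nil. The visible text attaches no test, margin or between-group interval to these results. The primary noninferiority tests use post-20vPnC titers with the baseline titer as covariate and are untouched.

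The conclusion assumes that Visit 1 titers are balanced between groups. Randomization gives this in expectation, and it should hold approximately in the evaluable population, whose vaccination criteria differ somewhat by group.

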3.2.2. Secondary SIIV Immunogenicity Endpoint

- Strain-specific HAI titers and fold rises in HAI titers from before vaccination to 1 month after vaccination with SIIV
 - The fold rises will be the ratio of HAI titers at Visit 2 to Visit 1 for both vaccine groups.

CCI [REDACTED]

[REDACTED]

[REDACTED]

[REDACTED]

[REDACTED]

[REDACTED]

[REDACTED]

[REDACTED]

[REDACTED]

3.4. Baseline and Other Variables

Day 1 is defined as the day of vaccination at Visit 1. Measurements or samples collected prior to vaccination on Day 1 are considered the baseline data for the assessments.

The following variables will be summarized as part of the baseline characteristics:

- Demographics
- Medical history

[REDACTED]

[REDACTED]

Other variables to be summarized include the following:

- CCI [REDACTED]
- Nonstudy vaccines
- Concomitant medications to treat SAEs or NDCMCs

[REDACTED]

[REDACTED]

3.4.1. Demographics, CCI [REDACTED] Medical History, CCI [REDACTED] CCI [REDACTED]

The demographic variables are age at vaccination at Visit 1 (in years), sex (male or female), race (black or African American, American Indian or Alaska native, Asian, Native Hawaiian or other Pacific Islander, white, multiracial, and not reported), and ethnicity (Hispanic or Latino or of Spanish origin, not Hispanic or Latino or of Spanish origin, not reported). In cases where more than 1 category is selected for race, the participant would be counted under the category “multiracial” for analysis.

Age at the first vaccination in years will be derived based on the participant’s birthday. For example, if the vaccination date is 1 day before the participant’s 70th birthday, the participant is considered to be 69 years old. For participants who were randomized but not vaccinated, the randomization date will be used in place of the date of the first vaccination for age calculation. If the randomization date is also missing, then the informed consent date will be used for age calculation.

CCI [REDACTED]

[REDACTED]

Medical history will be categorized according to MedDRA. Significant findings from any physical examination performed at baseline will also be collected on the Medical History page of the CRF and summarized with medical history.

CCI [REDACTED]

3.4.3. Nonstudy Vaccines and Concomitant Medications

The name and date of administration of CCI all nonstudy vaccinations received from the time of signing of the ICD to Visit 3, will be summarized. Concomitant medications will be recorded only if they were used to treat SAEs or NDCMCs from the time of signing of the ICD to Visit 4. Concomitant and prior vaccines and concomitant medications will be coded using the WHO Drug Dictionary.

3.5. Safety Endpoints

Local reactions, systemic events, AEs, SAEs, and NDCMCs have been described above (Section 3.1.1) in the primary safety endpoints.

4. ANALYSIS SETS (POPULATIONS FOR ANALYSIS)

Analysis populations are defined for the statistical analysis of safety and immunogenicity results in the table below. For the specified criteria in each population definition that are not associated with unblinded information (randomized or actual received vaccination), data for all participants will be assessed to determine if participants meet the criteria for inclusion in each analysis population prior to unblinding and releasing the database for the specified analysis, and the classifications will be documented per standard operating procedures.

Population	Description
Enrolled	All participants who sign the ICD.
Randomized	All participants who are assigned a randomization number in the IWR system.
Evaluable pneumococcal immunogenicity	All randomized participants who 
 receive the assigned investigational products at Visit 1 for the (SIIV+20vPnC)/saline group or receive the assigned investigational products at both Visit 1 and Visit 2 for the (SIIV+saline)/20vPnC group have the blood collection within 27 to 49 days after 20vPnC (Visit 2 for the [SIIV+20vPnC]/saline group, Visit 3 for the [SIIV+saline]/20vPnC group) have at least 1 valid OPA result from the blood sample collected 1 month after vaccination with 20vPnC have no other major protocol deviations as determined by the clinician
Evaluable HAI immunogenicity	All randomized participants who 
 receive the assigned investigational products at Visit 1 have the Visit 2 blood collection within 27 to 49 days after vaccination with SIIV have at least 1 valid HAI titer for any of the HAI strains in SIIV at Visit 2

Population	Description
	
 have no other major protocol deviations as determined by the clinician

 

	CCI 

Safety	All randomized participants who receive 1 dose of 20vPnC or SIIV or saline and have safety follow-up after any dose.

The statistical analysis of immunogenicity results will be primarily based on the evaluable immunogenicity populations, ie, the evaluable pneumococcal immunogenicity population for OPA titers and the evaluable HAI immunogenicity population for HAI titers.

CCI

All safety analyses will be based on the safety population. Participants will be summarized by vaccine group according to the investigational products they actually receive.

